5.2 Allogeneic Hematopoietic Stem Cell Transplantation

- 5.2.1 Flu/Bu2 RIC Transplant: The reduced intensity conditioning regimen will consist of fludarabine (120 mg/m² total) and low dose intravenous busulfan (6.4 mg/kg total). Fludarabine 30 mg/m²/d will be administered as a bolus intravenous infusion once a day for 4 days on days -5, -4, -3,-2 (based on actual body weight). Busulfan 0.8 mg/kg (based on actual body weight) will be administered intravenously twice daily (approximately 12 hours apart) on day-5,-4,-3,-2 for a total of 8 doses. Since it is dose twice daily, it is suggested that the busulfan be administered first, with the fludarabine dose sandwiched in between. Fludarabine and busulfan can be diluted per institutional practice. The rate of the fludarabine and busulfan infusions can be done according to institutional practice. In conjunction with chemotherapy, patients will receive pre-hydration and intravenous fluids and/or diuretics as needed, and antiemetics as per institutional guidelines. Day 0 is defined as the first day of infusion of donor PBSC (or bone marrow). In instances where the donor product arrival is delayed, the day 0 of transplant may be pushed back a day. Donor PBSC or marrow cells will be administered according to standard practice. For PBSC products, the stem cell dose will be a minimum of 2x10⁶, with a recommended target of 5x10⁶ CD34+ cells/kg. For marrow products, the recommended target is 2 x 10⁸ TNC/kg.Following stem cell infusion, RIC SCT patients will receive GM-CSF 500 mcg SC qd starting on day +1, until absolute neutrophil count is>1000 on 2 consecutive values over 2 or more days. GM-CSF may be held if patient has circulating blasts, develops severe bone pain, or at the discretion of the transplant MD based on clinical judgment. Levofloxacin 500mg PO QD (or 250mg PO QD if CrCl < 50) or another antibiotic is recommended as bacterial prophylaxis until ANC is >500 μL. Prophylactic antibiotics for Pneumocystis carinii and HSV/VZV will be administered as per standard institutional guideline for RIC SCT. CMV PCR surveillance and preemptive therapy for reactivation should follow standard institutional guideline.
- 5.2.2 Flu/Bu4 Myeloablative transplantation- The myeloablative conditioning regimen will consist of Fludarabine and high dose intravenous Busulfan approximately q6hrs for 4 days, as follows:
 - Fludarabine 40 mg/m² per day will be administered as a bolus infusion administered by IV infusion over approximately 1 hour for 4 days on days -5, -4, -3, -2 (based on actual body weight; or adjusted ideal body weight for those >125% of ideal body weight). Adjusted ideal body weight will be defined as ideal weight plus 25% of the difference between ideal and actual weight). Fludarabine can be diluted per institutional practice.

AIBW = IBW + (0.25)(ABW-IBW)

AIBW – adjusted ideal body weight

IBW – ideal body weight

ABW – actual body weight

5.2.2.2 **Busulfan** 0.8mg/kg will be administered intravenously 4 times daily (approximately q6hrs apart) for 5 days on day -5,-4,-3,-2, -1 for a total of 16 doses, as per institutional guidelines. The rate of the busulfan infusions can be done according to institutional practice. Dosing of busulfan will be based on actual body weight, or adjusted ideal body weight for patients >125% of ideal body weight. Adjusted ideal body weight be defined as ideal weight plus 25% of the difference between ideal and actual weight.

AIBW = IBW + (0.25)(ABW-IBW)

AIBW – adjusted ideal body weight

IBW – ideal body weight

ABW – actual body weight

In conjunction with chemotherapy, patients will receive seizure prophylaxis with Keppra from day -5 until day-1. Pre-hydration and intravenous fluids and/or diuretics will be as per the HSCT standard practice. Anti-emetics will be as per institutional guidelines.

The donor PBSC (or bone marrow) product will be infused on day 0. In instances where the donor product arrival is delayed, the day 0 of transplant may be pushed back a day. Stem cells will be administered according to standard practice. Stem cell dose will be a minimum of 2 x 10⁶, with a recommended target of 5x 10⁶ CD34+ cells/kg. GM-CSF will be given to hasten white blood count recovery starting on day+12, until absolute neutrophil count (ANC) is >1000/ul on 2 consecutive values over 2 or more days. GM-CSF may be held if ANC is already > 500 on day +12 or at the discretion of the treating physician based on clinical judgment. Infection prophylaxis for herpes viruses and *Pneumocystis carinii* will follow standard institutional practice. CMV PCR surveillance and preemptive therapy for reactivation should follow standard institutional guideline.

- 5.2.3 **GVHD prophylaxis:** GVHD prophylaxis for both myeloablative or RIC HSCT will include oral tacrolimus starting on day –3, and methotrexate on Days +1,3,6,11, as follows:
 - 5.2.3.1 **Tacrolimus (FK506)** will be given orally at a dose of 0.05 mg/kg PO bid starting day –3. Subsequent dosing will be based on clinical toxicity, and trough blood levels with recommended target of 5-10 ng/ml. Doses may be rounded to the nearest 0.5 mg dose and adjusted as needed to maintain therapeutic serum tacrolimus levels. The dose may be replaced if the patient vomits within 15 minutes of taking a dose, at the discretion of the transplant physician. Tacrolimus may be switched to intravenous dosing to maintain the same therapeutic goal level if necessary.

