6.1.1.9 Anticipated Toxicities of Allogeneic transplantation

Fludarabine- The most common adverse events include myelosuppression (neutropenia, thrombocytopenia and anemia), fever and chills, infection, and nausea and vomiting. Other commonly reported events include malaise, fatigue, anorexia, and weakness. Serious opportunistic infections have occurred in CLL patients treated with fludarabine.

Busulfan- The most frequent, serious, toxic effect of busulfan is myelosuppression resulting in leukopenia, thrombocytopenia, and anemia. Hepatic veno-occlusive disease, which may be life-threatening, has been reported following the use of very high doses of busulfan in combination with cyclophosphamide or other chemotherapeutic agents prior to bone marrow transplantation. Possible risk factors for the development of hepatic veno-occlusive disease include: total busulfan dose exceeding 16 mg/kg based on ideal

body weight, high busulfan levels, and concurrent use of multiple alkylating agents. A clear cause-and-effect relationship with busulfan has not been demonstrated. At high doses, busulfan has been shown to induce clinical seizures, and as such, all patients will receive seizure prophylaxis during conditioning with high dose busulfan. Interstitial pulmonary fibrosis has been reported rarely. Busulfan is capable of inducing cataracts in rats and there have been several reports indicating that this is a rare complication in humans. In the few cases reported in humans, cataracts have occurred only after prolonged administration of busulfan. Hyperpigmentation is the most common adverse skin reaction and occurs in 5% to 10% of patients, particularly those with a dark complexion.

Tacrolimus - Primary toxicities include renal insufficiency, hypertension, hyperglycemia, hypomagnesemia, hypokalemia, and neurologic toxicity, including seizure and visual blindness. Rarely, tacrolimus may thrombotic microangiopathy, a severe condition characterized by acute renal failure, neurologic symptoms (confusion, seizures), anemia and thrombocytopenia.

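### The myeloablative busulfan order contradicts itself: four doses a day on five listed days is 20 doses, but the printed total and the four-day lead-in both give 16

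*Combined protocol and SAP*

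**What the plan says.** Section 5.2.2 introduces the myeloablative regimen as fludarabine with "high dose intravenous Busulfan approximately q6hrs for 4 days". Section 5.2.2.2 then gives the operative order, 0.8 mg/kg per dose, "4 times daily (approximately q6hrs apart) for 5 days on day -5,-4,-3,-2, -1 for a total of 16 doses", and defers to institutional guidelines. It states no total in mg/kg. Donor cells follow on the next calendar date: "The donor PBSC (or bone marrow) product will be infused on day 0". Seizure prophylaxis in the same section covers day -5 to day -1.

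The reduced-intensity order in section 5.2.1 has the same form: 0.8 mg/kg "twice daily (approximately 12 hours apart) on day-5,-4,-3,-2 for a total of 8 doses". That section does print a total, 6.4 mg/kg.

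On dosing weight, section 5.2.2.2 says: "Dosing of busulfan will be based on actual body weight, or adjusted ideal body weight for patients >125% of ideal body weight". Adjusted weight is ideal weight plus a quarter of the difference between actual and ideal.

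Section 6.1.1.9 lists, among possible risk factors for hepatic veno-occlusive disease, a "total busulfan dose exceeding 16 mg/kg based on ideal" body weight. It adds that a "clear cause-and-effect relationship with busulfan has not been demonstrated".

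**The concern.** The Flu/Bu4 sentence specifies frequency, number of days, calendar days and number of doses, and these cannot all hold if each listed day carries four doses. The section also gives two durations for the same course, four days in the lead-in and five in the order.

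This is a patient-safety matter and not an inferential one. Someone who builds an order from the frequency and the day list would prescribe four doses more than the stated total. No mg/kg total is printed for this regimen against which the mistake could be caught, whereas Flu/Bu2 has one.

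**Working it through.** **Inputs.** Dose 0.8 mg/kg; four a day; five listed days; stated total 16 doses (all 5.2.2.2). Four-day duration (5.2.2 lead-in). Flu/Bu2: two a day, four listed days, 8 doses, 6.4 mg/kg (5.2.1). Weight rule (5.2.2.2). The 16 mg/kg figure (6.1.1.9).

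**Step 1: dose counts.** Doses = doses per day × days; total = doses × 0.8 mg/kg.

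| Reading | Doses | Total | Agrees with the stated figure? |
|---|---|---|---|
| Flu/Bu2, as written | 2 × 4 = 8 | 6.4 mg/kg | Yes: 8 doses, 6.4 mg/kg |
| Flu/Bu4, lead-in (4 days) | 4 × 4 = 16 | 12.8 mg/kg | Yes: 16 doses |
| Flu/Bu4, order read literally (5 days) | 4 × 5 = 20 | 16.0 mg/kg | No: 16 doses stated |

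The plan's figure of 16 is reproduced from the lead-in but not from the order. The literal reading adds 4 doses, or 3.2 mg/kg; 20/16 = 1.25, so 25% more. The Flu/Bu2 sentence multiplies out exactly, so the mismatch is specific to Flu/Bu4 and is not a counting convention of the document.

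**Step 2: can 16 doses reach five dates?** Let the first dose be at hour h on day -5, with doses every 6 hours.

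- Dose 16 falls at h + 15 × 6 = h + 90. Day -1 begins at hour 96, so the course reaches day -1 if h is 6 or later.
- A 06:00 start gives 3+4+4+4+1 doses over days -5 to -1. A noon start gives 2+4+4+4+2. A start before 06:00 gives 4+4+4+4 and ends on day -2.
- Dose 20 of a literal course falls at h + 19 × 6 = h + 114. Day 0 begins at hour 120, so with h at 6 or later the course runs into the day of donor cell infusion. A noon start gives 2+4+4+4+4, then 2 on day 0.
- With a start before 06:00, all 20 doses fit on days -5 to -1, so the calendar alone would not always expose the mistake.

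The five dates are therefore compatible with a 16-dose, 96-hour course that begins part-way through day -5.

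**Step 3: the size of a literal course against the figure in 6.1.1.9.** Let r = actual/ideal weight and d = dosing weight/ideal weight. Then d = r for r ≤ 1.25, and d = 1 + 0.25(r − 1) above that. The total per kg of ideal weight is 12.8d for 16 doses and 16.0d for 20.

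| Actual weight, % of ideal | d | 16 doses (mg/kg ideal) | 20 doses (mg/kg ideal) |
|---|---|---|---|
| 100 | 1.00 | 12.8 | 16.0 |
| 110 | 1.10 | 14.1 | 17.6 |
| 125 | 1.25 | 16.0 | 20.0 |
| just above 125 | 1.0625 | 13.6 | 17.0 |
| 150 | 1.125 | 14.4 | 18.0 |

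For 16 doses, 12.8d > 16 requires d > 1.25. Under the weight rule this happens only when 1 + 0.25(r − 1) > 1.25, that is r > 2.0. For 20 doses, 16.0d > 16 requires only r > 1.0. So the stated course exceeds the figure only above 200% of ideal weight, while a literal five-day course exceeds it in anyone above ideal weight.

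**The case against.** The strongest reply is that the total is not wrong; only the schedule wording is loose. The count of 16 stands in the same sentence as the day list, and the lead-in independently gives 16. If the course starts part-way through day -5, then dose, interval, dates and total all agree, and only the phrase giving a five-day duration is at fault. Seizure prophylaxis to day -1 suggests that the fifth date was deliberate. To give 20 doses, a reader would have to disregard the printed count, and institutional practice is a further control. The veno-occlusive comparison concerns an improbable course. Section 6.1.1.9 gives no route for the 16 mg/kg figure, discusses very high doses combined with other agents, and disclaims causation. Nothing here touches the trial's inference.

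Most of this stands. Sixteen doses are very probably meant, a 20-dose order is unlikely, and the veno-occlusive figure indicates scale without predicting harm. At exactly ideal weight a 20-dose course equals the figure and does not exceed it.

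Two things do not follow. First, the partial-day explanation has to be supplied by the reader; the text orders four doses daily for five days, which says the opposite. The prophylaxis dates would fit either course. Second, deferring to institutional guidelines does not settle a conflict between a frequency, a day list and a count that the protocol itself prescribes for three centers.

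**Conclusion.** The concern holds. As written, the Flu/Bu4 busulfan order gives 20 doses (16.0 mg/kg of dosing weight) by its frequency and days, against 16 doses (12.8 mg/kg) by its printed total and by the lead-in: a 25% difference in a cytotoxic dose. The arithmetic uses protocol figures only. That 16 doses are intended is an inference, though a strong one. That the fifth date reflects a start at 06:00 or later on day -5 is a plausible assumption which the protocol does not state.

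The probability of harm is low, the potential harm is serious and the correction is trivial, so this should be fixed. Conditioning is common to both arms, so sample size, power, stratification and the primary analysis are unaffected.

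**What to change.** Replace the schedule wording in 5.2.2.2 with, for example:

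> Busulfan 0.8 mg/kg IV approximately every 6 hours for 16 doses (12.8 mg/kg total) over 4 days (96 hours), starting on day -5 and ending on day -2 or day -1 depending on start time.

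The transplant investigators should confirm the intended course first. Day -1 need not be deleted, because a 16-dose course can legitimately reach it. The reference to institutional guidelines can stay. Printing the mg/kg total supplies the cross-check that Flu/Bu2 already has.

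The cost is a one-sentence protocol clarification, with no statistical consequence.

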5.2.3.2 Methotrexate

For the RIC cohort (FluBu2)- The methotrexate dose will be 5 mg/m² IV on day+1,3,6,11, infused as per standard institutional guidelines. In cases where stem cell infusion (day 0) spans more than 1 day, the day +1 dose of methotrexate

should start 1 day after the end of the SC infusion.

For the Myeloablative cohort (FluBu4)- The methotrexate dose will be 15 mg/m² IV on day +1, and 10mg/m² on days +3,6, and 11. Methotrexate should be infused as per standard institutional guidelines. In cases where stem cell infusion (day 0) spans more than 1 day, the day +1 dose of methotrexate should start 1 day after the end of the stem cell (SC) infusion. Leucovorin rescue is allowed per standard practice guidelines if necessary, at the discretion of the transplant physician. The day 11 dose of MTX may be reduced 50% or omitted if deemed necessary based on the clinical situation, and at the discretion of the transplant physician. In cases where clinical toxicities, e.g. renal failure, pleural effusion, etc. would render completing at least 3 doses of methotrexate unsafe, substitution with mycophenolate mofetil (cellcept) 1000mg PO/IV BID or other agent such as sirolimus is allowed at the discretion of the treating physician. In instances where MTX is substituted by cellcept, it is recommended that the cellcept be discontinued around day +28 in the absence of GVHD.

5.2.4 Tacrolimus Taper:

- 5.2.4.1 Tacrolimus taper is NOT allowed during the vaccination period. Taper may commence 1 week after the last GVAX/Placebo vaccine, at the discretion of the transplant physician, with the goal to be off immune suppression by 6-9 months in the absence of GVHD.
- 5.2.4.2 **Tacrolimus taper for patients with progressive disease before completion of vaccinations**: Patients with evidence of progressive disease AND requiring additional therapy or taper of immune suppression will receive no further vaccinations. In these cases, the tacrolimus taper will be performed at the discretion of the treating physician.

5.3 GVAX/Placebo Vaccination

Vaccination with GVAX or placebo vaccine will commence after hematologic recovery has occurred and the patient is between day +30 to day +60* post transplant. Vaccine administration can occur on an either inpatient or outpatient basis. At any time between day+30 to day +60*, the patient may undergo a bone marrow aspirate/biopsy and GVAX/placebo vaccination may commence provided the following criteria are satisfied:

* Day 60 or next business day, if day 60 occurs on a weekend or holiday

5.3.1 Criteria for starting GVAX/Placebo administration:

- No grade II-IV acute GVHD
- No systemic corticosteroid therapy*
- No uncontrolled acute infection
- No CTC grade ≥ 3 non-hematologic toxicity
- Absolute neutrophil count $\geq 500/\text{ul}$ off growth factor

- Platelet count ≥ 10 K/ul without transfusion.
- Absolute eosinophil count ≤ 5000/ul

Participants who do not meet the above criteria to start vaccination by day +60 will be considered "off treatment", and followed for survival.

5.3.2 **GVAX/Placebo Administration:**

- 5.3.2.1 Vaccinations will be administered weekly x 3 weeks, then q2weeks x 6 weeks for a total of 6 vaccines. The weekly scheduling of vaccination can be +/- 2 days for scheduling flexibility. A physician, PA, NP, RN, or research RN can administer the injections in either an outpatient or inpatient clinical setting. Injections will be administered according to standard nursing procedure in the patient's arms and thighs on a rotating basis. Injections must be performed without the prior application of EMLA or other topical or local anesthetics, as such compounds both could obscure local reactions to the vaccination and could cause reactions that might be interpreted as vaccine reactions. Approximately half of the vaccine dose should be administered subcutaneously, and remaining half the vaccine dose intradermally. It is suggested that about half of the vaccine be given first intradermally, and the rest subcutaneously by changing that angle of the needle.
- 5.3.2.2 Information regarding the number and location of the injections, the date of vaccination, route of administration, total volume of vaccine administered and vaccine site injection reactions will be collected for each vaccination and recorded in the patient medical record.
- 5.3.2.3 A skin punch biopsy of the vaccine site is strongly encouraged (but not required) for histologic and laboratory correlative examination 2-3 days after the 1st and 5th vaccination. Skin punch biopsies will be sent to DFCI.
- 5.3.2.4 The Vaccine Specific Toxicity Form (Appendix I) must be completed by a study investigator at weekly during vaccination period, and at 1 month after the last vaccination.

5.3.3 Early discontinuation of GVAX/Placebo vaccination

- 5.3.3.1 Disease relapse or progression requiring taper or withdrawal of tacrolimus, or additional systemic therapy.
- 5.3.3.2 Acute GVHD or chronic GVHD requiring systemic steroid therapy.
- 5.3.3.3 CTC grade ≥ 4 non-hematologic toxicity possibly, probably or definitely related to vaccination.
- 5.3.3.4 Delay of vaccination over 14 days (see below)

^{*} Except for physiologic doses of steroids for adrenal insufficiency

- 5.3.4 **Delay of GVAX/Placebo vaccination**: If severe hematologic toxicity (defined as ANC <500/ul, platelet < 10K/ul, or absolute eosinophil count > 5000/ul), CTC grade ≥ 3 non-hematologic toxicity develops during the vaccination period, vaccination may be delayed up to 14 days until the event has improved by at least 1 CTC grade. If condition is not improved after 14 days in the opinion of the treating physician and/or study PI, or if the toxicity recurs upon reinitiation of vaccination, no further vaccination will be given. In an event where the toxicity is grade < 3, vaccination may also be delayed at the physician's discretion.
- 5.3.5 **Off Treatment Criteria with continued study visits**: Patients who receive at least 1 vaccination, but do not complete 6 vaccines for any reason other than disease relapse requiring additional therapy or hospice will be considered "off treatment". These patients will continue "on study" for study visits, tests/procedures, and assessment of toxicity and survival end points. It is preferred that study specific blood samples be drawn and bone marrow biopsies are performed according to the study calendar, but these may be foregone for clinical reasons or if the patient declines to have one performed.
- 5.3.6 **Off Treatment Criteria with survival follow-up only**: Patients meeting the following criteria will be considered "off treatment" and no further study visits, or study related testing will be performed. Survival information will be recorded.
 - 5.3.6.1 Patients who have disease relapse after starting vaccination and require additional therapy (chemotherapy or immune therapy) or hospice placement.

5.4 General Concomitant Medication and Supportive Care Guidelines

Guidelines for use of concomitant medications, and supportive care medications should follow standard practice for patients after allogeneic stem cell transplantation.

- Growth factor (G-SCF or GM-CSF) use to stimulate white blood cells during the vaccination period is not allowed during weeks where patients are scheduled to receive vaccinations. This may be given on weeks during the vaccination period where no vaccinations are given.
- As described above, patients should remain on tacrolimus without active taper during the vaccination period. Routine adjustment of tacrolimus dosing to maintain trough level in therapeutic range should be performed as per standard of practice.
- Addition of other systemic immune suppressive medications, including steroids, for the treatment graft-versus-host disease will lead to discontinuation of vaccination.
- Short term use of systemic steroids, such as for blood or platelet transfusion reactions, hives, or other acute allergic reaction is allowed.

5.5 Duration of Vaccination

Duration of vaccination will depend on individual response, evidence of disease progression and tolerance. In the absence of treatment delays due to adverse events, treatment may continue for administration of all 6 vaccines or until one of the following criteria applies:

General:

- Intercurrent illness that prevents further administration of the vaccine
- Unacceptable adverse event(s),
- Participant demonstrates an inability or unwillingness to comply with the regimen and/or documentation requirements
- Participant decides to withdraw from the study, or
- General or specific changes in the participant's condition render the participant unacceptable for further treatment in the opinion of the treating investigator.
- GVAX discontinuation based on criteria as set previously.

5.6 Duration of Follow Up

Because this is a gene transfer study, all participants who received at least one vaccination will be followed for safety for up to 15 years after removal from study, or until death, whichever occurs first. Participants removed from study for unacceptable adverse events will be followed until resolution or stabilization of the adverse event.

